11.6 Management of Toxicity and Hypersensitivity Reactions

Patients are typically assessed by both the ward nursing staff and by specialist pain nurses for signs of local anaesthetic hypersensitivity or systemic toxicity. Signs/symptoms of hypersensitivity may include new rash, facial swelling, nasal congestion, shortness of breath, coughing, wheezing, vomiting and diarrhoea, dizziness, hypotension, seizure, loss of consciousness, respiratory arrest. Signs/symptoms of local anaesthetic systemic toxicity include agitation, acute delirium, dizziness, drowsiness, tinnitus, perioral hypoaesthesia, metallic taste, dysarthria, seizures, arrhythmia, hypotension, respiratory arrest, cardiac arrest.

If local anaesthetic hypersensitivity or systemic toxicity is suspected, the infusion must be stopped immediately, and the on-call anaesthetic team contacted. If the participant is in cardiac arrest, cardiopulmonary resuscitation must commence. Alternatively, if the participant has a cardiac output, 100% oxygen should be administered, and the airway secured, as necessary. IV access needs to be confirmed or established. Seizures should be addressed quickly, and treatment options include propofol. Cardiovascular system effects, such as arrhythmias, conduction block, and progressive hypotension and bradycardia, should be managed by conventional Advanced Life Support protocols.

Local anaesthetic toxicity would be considered a SAR and would be reported within 24 hours (see Section 13 on Pharmacovigilance).

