5.4 Secondary Outcomes measures

Secondary outcome measures:

(First 5 postoperative days)

- Participant satisfaction related to pain management during the preceding 24 h, assessed preoperatively and once daily postoperatively for up to five days using a 4-point Likert scale
- Opioid use assessed once daily postoperatively for five days, converted to morphine equivalents using the University of Alberta Multidisciplinary Pain Centre Opioid Conversion Guide (54)
- Opioid side effects (frequency and severity of symptoms) assessed once daily postoperatively for five days

(At discharge)

- Morbidity, assessed using Clavien-Dindo grading at discharge
- Length of hospital stay

(At 30 days)

Surgical site infection rates classified as per the 2008 CDC/NHSN document assessed at 30 days (55)

(At 90 days)

• Days alive and out of hospital assessed at 90 days (DAOH-90)

(At 3 to 6 months)

- Chronic residual limb pain assessed at 3 and 6 months
- Phantom limb pain assessed at 3 and 6 months
- Length of hospital stay assessed at 3 and 6 months
- Residual limb surgery assessed at 30 days, 3 months, and 6 months
- Health-related QoL assessed using EQ-5D-5L at 3 months and 6 months
- Participant reported anxiety and depression assessed using HADS at 3 months and 6 months
- Prosthesis fitting assessed as rate and time to fitting using SIGAM at 3 and 6 months
- Assessment of health care resource usage during the first 6 months postoperatively
- Mortality assessed at 6 months.

6 Trial Design and Setting

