11.1 Treatment(s)

In participants randomised to the intervention arm, a PNC is inserted adjacent to the cut end of the major nerve (either sciatic nerve for AKAs, or tibial nerve for BKA/TKAs) and tunnelled externally before being connected to a local anaesthetic infusion device delivering local anaesthetic via an elastomeric or electronic pump for up to five days. Participants randomised to the control arm will not have a PNC inserted during their MLLA.

The placement of the PNC is rapid to learn for surgeons who are not already trained in the technique. All surgeons involved in placing a PNC will undergo training according to the Standard Operating Procedure (SOP) for insertion of the perineural catheter and management of local anaesthetic infusion, to ensure the technique used is as homogenous as possible. An accompanying training presentation will illustrate the intervention. The important points are covered in Section 11.1.1 below.

All participants in both arms will receive 'best care' personalised pre-, intra-, and postoperative analgesia at the discretion of the treating medical teams. This may include patient-controlled, IV, and/or oral analgesia. Ultrasound-guided nerve blocks and catheters (e.g., to the femoral nerve), and injections of local anaesthetic directly into/around the nerve at the time of surgery, are permitted in either arm.

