12.1.3 Daily Postoperative Assessment

For the first five postoperative days, routine assessments will consist of:

- Pain scores, assessed twice daily (am and pm, separated by ≥4 hours), using NRS
- Participant satisfaction related to pain management during the preceding 24 h, assessed once daily using a 4-point Likert scale (with am pain score for amputations completed in the morning and pm pain score for amputations completed in the afternoon)
- Total opioid use, converted to morphine equivalents (54)
- Frequency and severity of opioid side effects (61)
- Duration PNC remains in place
- Duration of delivery of local anaesthetic
- Analgesic use, including opioid, paracetamol, non-steroidal and neuropathic pain agent (gabapentin, pregabalin, amitriptyline) use. For participants in the treatment arm, amount of local anaesthetic infused will also be recorded.

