13.2 Trial Specific SAE Reporting requirements

In addition to the SAE reporting requirements defined in Table 3, for the purposes of this trial the following events will also be considered SAEs and must be captured on the SAE form and reported to the CTR with 24 hours of knowledge of the event:

- Infection around PNC exit site
- Local anaesthetic toxicity reactions (see Section 11.6)

For the purposes of this trial the following events will **not** require reporting as SAEs:

• AEs as a result of surgical complications of CTCAE grades 1 and 2 as listed in the protocol (Table 6, page 64 - 65)

These should be completed in the participant's notes and on the relevant CRF page and forwarded

to the CTR in the normal timeframes for CRFs.

Pre-existing conditions should only be reported if they met the definitions for an SAE and if the condition worsens by at least one CTCAE grade.

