4.2 Posology and method of administration

Levobupivacaine should be administered only by, or under the supervision of, a clinician having the necessary training and experience.

Chirocaine Solution for Infusion is for epidural use only. It must not be used for intravenous administration.

Type of Block	Concentration	Infusion Rate Per Hour	
	mg/ml	ml	mg
Continuous Infusion:			
Post-operative pain management	1.25	10-15	12.5-18.75
Lumbar epidural (analgesia in labour)	1.25	4-10	5-12.5

Careful aspiration before infusion is recommended to prevent intravascular injection. If toxic symptoms occur, the injection should be stopped immediately.

There is limited safety experience with levobupivacaine therapy for periods exceeding 24 hours. In order to minimise the risk for severe neurological complications, the patient and the duration of administration of levobupivacaine should be closely monitored (see section 4.4).

Maximum dose

The maximum dosage must be determined by evaluating the size and physical status of the patient. The maximum recommended dose during a 24 hour period is 400 mg.

For post-operative pain management, the dose should not exceed 18.75 mg/hour, however the accumulated dose for a 24 hour period should not exceed 400 mg. For labour analgesia by epidural infusion, the dose should not exceed 12.5 mg/ hour.

Paediatric population

The safety and efficacy of levobupivacaine in children for pain management has not been established.

Special Populations

Debilitated, elderly or acutely ill patients should be given reduced doses of levobupivacaine commensurate with their physical status.

In the management of post-operative pain, the dose given during surgery must be taken into account.

There are no relevant data in patients with hepatic impairment (see sections 4.4 and 5.2).

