Epidural anaesthesia with any local anaesthetic may cause hypotension and bradycardia. All patients must have intravenous access established. The availability of appropriate fluids, vasopressors, anaesthetics with anticonvulsant properties, myorelaxants, and atropine, resuscitation equipment and expertise must be ensured (see section 4.9).

Epidural Analgesia

There have been post-marketing reports of cauda equina syndrome and events indicative of neurotoxicity (see section 4.8) temporally associated with the use of levobupivacaine for 24 hours or more for epidural analgesia. These events were more severe and in some cases led to permanent sequelae when levobupivacaine was administered for more than 24 hours. Therefore, infusion of levobupivacaine for a period exceeding 24 hours should be considered carefully and only be used when benefit to the patient outweighs the risk.

It is essential that aspiration for blood or cerebrospinal fluid (where applicable) be done prior to injecting any local anaesthetic, both before the original dose and all subsequent doses, to avoid intravascular or intrathecal injection. However, a negative aspiration does not ensure against intravascular or intrathecal injection. Levobupivacaine should be used with caution in patients receiving other local anaesthetics or agents structurally related to amide-type local anaesthetics, since the toxic effects of these drugs are additive.

Special populations

Debilitated, elderly or acutely ill patients: levobupivacaine should be used with caution in debilitated, elderly or acutely ill patients (see section 4.2).

Hepatic impairment: since levobupivacaine is metabolised in the liver, it should be used cautiously in patients with liver disease or with reduced liver blood flow e.g. alcoholics or cirrhotics (see section 5.2).

This medicinal product contains 3.5mg/ml sodium in the bag or ampoule solution to be taken into consideration by patients on a controlled sodium diet.

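### Opioid side effects are elicited daily in both arms, but the local anaesthetic toxicity signs in section 11.6 have no scheduled record, so the two harms are not comparably ascertained

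*Protocol*

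**What the plan says.** Opioid harm is a secondary outcome in Protocol 5.4: "Opioid side effects (frequency and severity of symptoms) assessed once daily postoperatively for five days". It is on the daily list in 12.1.3, is participant reported on a CRF in both arms (Table 2, row 22), and has its own analysis line in Table 8.

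Local anaesthetic harm is handled differently. Section 11.6 lists the signs of hypersensitivity and systemic toxicity and requires the infusion to stop on suspicion, but on detection it says: "Patients are typically assessed by both the ward nursing staff and by specialist pain nurses for signs of local anaesthetic hypersensitivity or systemic toxicity". It then adds: "Local anaesthetic toxicity would be considered a SAR and would be reported within 24 hours". Section 13.2 repeats this by naming toxicity reactions as trial-specific SAEs. Section 12.1.3 records how long the catheter stays in, how long local anaesthetic is delivered and how much is infused. It does not record the signs in 11.6. Table 2 has only general rows for adverse effects and for SAEs/SARs, both completed as required.

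The infusion runs "via an elastomeric or electronic pump for up to five days" (11.1). In Appendix 1, section 4.2 of the levobupivacaine SmPC says safety experience beyond 24 hours is limited and that "the patient and the duration of administration of levobupivacaine should be closely monitored". Under epidural analgesia, its section 4.4 says that "infusion of levobupivacaine for a period exceeding 24 hours should be considered carefully and only be used when benefit to the patient outweighs the risk". Protocol 11.5 restates several of the manufacturers' cautions but not this one.

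**The concern.** The catheter is expected to lower opioid use and may therefore lower opioid side effects. Local anaesthetic toxicity is the harm specific to the infusion. The first is asked about on a schedule. The second is recorded only if somebody notices it and names it. A comparison of harms built on these two sources mixes active and passive ascertainment, and the IDMC, which under 22.4 monitors both safety and benefit, would see the same mixture. The trial is also open label (14.2), so how closely unscheduled signs are looked for may differ between arms.

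The reporting rules add to the problem. If a mild sign is noticed, the protocol gives more than one answer on whether it is an SAE or a routine form entry.

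**Working it through.** The plan gives no figure for toxicity, so the check is mainly a comparison of passages, followed by a short illustration.

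**Scheduled symptom records, days 1 to 5, per participant**

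| | Opioid side effects | Signs listed in 11.6 |
|---|---|---|
| Item in 12.1.3 | Yes, daily | None |
| Row in Table 2 | Row 22, daily, both arms | None; adverse-event rows as required |
| Line in Table 8 | Yes | None |
| Scheduled records | 5 | 0 |
| Rule once recognised | No specific rule | SAE form within 24 hours (11.6, 13.2) |

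Over the trial this is at most 650 × 5 = 3,250 opioid symptom records against none for the 11.6 signs. These are counts of form entries, not of missed harm. The 24-hour clock in 13.2 starts at knowledge of the event, so it does not replace detection.

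**Overlap between 11.6 and Table 6.** Section 11.6 lists 13 signs of systemic toxicity. Seven of them (agitation, delirium, dizziness, tinnitus, dysarthria, seizure, hypotension) are also in Table 6 as expected events of amputation.
- 13.2 exempts Table 6 events of grade 1 and 2 from SAE reporting when they are put down to surgery. The same mild sign is therefore a 24-hour SAE or a routine entry, depending on attribution alone.
- 13.4 goes further: anticipated treatment-related events of grade 2 or below are outside expedited reporting and go on a CRF in the usual timeframe. That conflicts with 11.6 and 13.2, which send toxicity reactions to 24-hour reporting without regard to grade.

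**Illustration under assumed rates.** The size of the catheter arm comes from the plan's own calculation, which reproduces: 61.7% × 1.2 = 74.04%; 90% power at two-sided 5% gives 299 per arm; 299 / 0.92 = 325; 2 × 325 = 650. The documents give no toxicity rate and no capture rate, so both are assumptions. With true rate r and capture proportion s, the probability that no event is recorded is (1 − r·s)^325.

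| Assumed r | Expected events (325 × r) | P(none recorded), s = 1 | P(none recorded), s = 0.5 |
|---|---|---|---|
| 0.5% | 1.6 | 0.20 | 0.44 |
| 1% | 3.3 | 0.04 | 0.20 |
| 2% | 6.5 | 0.001 | 0.04 |

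Even with full capture, zero events in 325 leaves an upper 95% bound of 1 − 0.05^(1/325) = 0.92%. Incomplete capture could therefore matter for an uncommon harm, but the table shows sensitivity to assumptions and is not an estimate for this trial.

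**The case against.** The best defence is that the protocol is stricter on local anaesthetic toxicity than on opioid effects. Every recognised reaction is an SAE whatever its seriousness, the SAE window runs to postoperative day 7 and SARs are reported to the end of follow-up (13.5.1). Exposure is recorded daily on a catheter monitoring CRF (Table 2, row 23). Exit-site infection is also a mandatory SAE, and surgical site infection, graded complications, phantom pain and stump pain are collected in both arms. All of this stands. It means that severe toxicity and most other catheter harms are covered, and it confines the point to milder signs.

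It can also be said that the SOP on managing the infusion, or the catheter monitoring CRF, neither of which is shown, may contain a symptom check. That is possible. But row 23 applies to the intervention arm only and is described as a fidelity measure, so a check placed there would give no comparison with control participants, who may also receive nerve blocks, nerve catheters or local anaesthetic injections (11.1).

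A reader might infer that the harm balance is tilted towards the catheter. The documents do not support that. Missed mild toxicity would favour the catheter, but dizziness or drowsiness caused by local anaesthetic and scored as an opioid effect would count against it. A reader might also infer that the five-day infusion breaches the SmPC. It is not shown to: the neurotoxicity reports there concern epidural use, the SmPC does not bar infusion beyond 24 hours, levobupivacaine is one of three permitted agents, 11.7 refers readers to the SmPCs, and 11.8 acknowledges off-licence use.

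**Conclusion.** The point holds as a gap in ascertainment and an inconsistency in reporting, not as a demonstrated bias. Scheduled symptom records are five per participant for opioid effects and none for the signs in 11.6, so mild toxicity is captured passively and the two harms cannot be compared on equal terms. Neither the direction nor the size of any resulting bias can be derived from the documents. Separately, 11.6 and 13.2 on one side, and 13.4 and the grade 1 to 2 exemption tied to Table 6 on the other, do not give one answer on how a mild toxicity sign is classified and reported. The SmPC statements on use beyond 24 hours are a matter for reconciliation only. The conclusion assumes that no unseen trial form already records these signs in both arms. It is a worthwhile, inexpensive improvement and does not touch the primary outcome or the sample size.

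**What to change.** - Add to 12.1.3 and Table 2 a once-daily yes/no record of the signs listed in 11.6, in both arms on days 1 to 5, taken at the existing daily assessment. Tabulate it by arm for the IDMC and in the final report.
- Reconcile 11.6, 13.2, 13.4 and Table 6 so that a mild sign of possible local anaesthetic toxicity has one classification and one reporting route.
- Reconcile 11.5 and the five-day infusion in 11.1 with the statements on use beyond 24 hours in the appended levobupivacaine SmPC, noting that the neurotoxicity reports there are epidural. Which dose, duration or monitoring rule should apply is for the sponsor's clinical team; nothing is proposed here.

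The cost is one short checklist on a form already completed at a contact already made, with no extra visits and no effect on the sample size. The downside is that a few more non-specific symptoms will be recorded in both arms.

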11.7 Prohibited Medications and Interaction with Other Drugs

Caution must be used in the administration of other local anaesthetics or agents structurally related to amide-type local anaesthetics, e.g., certain antiarrhythmics, such as lidocaine and mexiletine, since the systemic toxic effects are additive. While patients already taking these medications at time of enrolment will be excluded, use of them postoperatively must be undertaken with caution but is not specifically prohibited. Full information is available from the SmPC for Levobupivacaine, Ropivacaine and Bupivacaine which are attached as an appendix to this protocol.

There are no other specific prohibited medications, however caution must be used in the administration of local anaesthetic for other purposes to ensure that a maximum dose of the local

anaesthetic does not exceed recommended dose rates. The maximum doses should be reduced for patients who are acutely ill, elderly, debilitated or <60kg.

11.8 Accountability Procedures

No medications or associated equipment or consumables are being provided to sites as part of the trial, and therefore, sites are expected to use their own stock. No CTR accountability, recall and disposal procedures are required as described in the PLACEMENT IMP Management Plan. Sites should follow local governance for the off-license use of Levobupivacaine, Ropivacaine and Bupivacaine (i.e., via PNC). The PLACEMENT Trial SOP for insertion of the PNC should also be followed.

Local anaesthetic will be infused for up to five days postoperatively, and therefore, continuation of the IMP after completion of the trial is not applicable. Once participation in the trial has ended, any additional care is not expected to differ from what is normally expected for patients who have undergone MLLA for PAD +/- diabetes.

11.9 Compliance

Pls and other medically qualified staff who are deemed experienced and competent at inserting PNCs by the PI and have been delegated this responsibility as per the PLACEMENT delegation log, are required to watch the Training presentation and read the PLACEMENT Trial SOP for the insertion of PNCs. This training must be documented on the PLACEMENT Training log. The PLACEMENT Delegation and Training logs will be monitored by the CTR.

12 Trial Procedures

All participants will be enrolled in the trial for approximately six months, from pre-operative screening to 6-month postoperative follow-up. During the inpatient phase there is a pre-operative baseline assessment and daily postoperative assessments up to five days following the operation. If a member of the research team is unable to collect patient reported outcomes (PROs) (e.g., over the weekend), a member of the clinical team may be permitted to collect this data. If a member of the clinical team is unable to retrospectively captured from information in the clinical notes. Should pain scores be routinely captured, but not using an 11-point scale, we will permit conversion of clinical pain scores (with a range of none (0) – severe (3)) as per published conversion methods (18).

During follow-up there are two assessments, which may be conducted either via telephone, email, post or in person at 3 months and 6 months post randomisation.

12.1 Assessments

12.1.1 Baseline

The baseline assessment consists of collecting the following information:

- Preoperative pain assessed by the NRS
- Participant satisfaction of pain management during the preceding 24 h, assessed using a 4point Likert scale
- Preoperative opioid and analgesic use
- Health-Related QoL assessed using EQ-5D-5L (59)
- Depression measured by the Hospital Anxiety and Depression Scale (HADS) (60)
- Past surgical and medical history, including cigarette use and type of diabetes mellitus
- Health services contact
- Results from the routinely collected pre-operative blood tests, including liver and renal function tests
- Planned level of amputation
- Body weight
- Residential status on admission
- Review of pre-operative resting 12-lead ECG
- (For participants of child-bearing potential) Review of pre-operative pregnancy test result

12.1.2 At Operation

Operative assessment includes recording the following information:

- Method of anaesthesia
- Whether a pre-operative regional nerve block was performed, and if so, what this was and what drugs were used
- Whether the nerve was successfully identified
- Method used to cut the nerve and whether it was tied
- Level of amputation
- Fidelity of nerve catheter placement, specifically assessing successful placement of the nerve catheter at the time of surgery.

Providing that the nerve is successfully identified, the participant is either randomised at this point, or if randomisation has already been performed, allocation is revealed to the treating team, and the nerve catheter is placed if randomisation is to the treatment arm. If the nerve is not successfully identified, randomisation cannot take place and the participant's enrolment in the trial is terminated. Baseline and intra-operative data will be retained for analysis (providing the participant does not withdraw consent), but no further assessments will be performed.

12.1.3 Daily Postoperative Assessment

For the first five postoperative days, routine assessments will consist of:

- Pain scores, assessed twice daily (am and pm, separated by ≥4 hours), using NRS
- Participant satisfaction related to pain management during the preceding 24 h, assessed once daily using a 4-point Likert scale (with am pain score for amputations completed in the morning and pm pain score for amputations completed in the afternoon)
- Total opioid use, converted to morphine equivalents (54)
- Frequency and severity of opioid side effects (61)
- Duration PNC remains in place
- Duration of delivery of local anaesthetic
- Analgesic use, including opioid, paracetamol, non-steroidal and neuropathic pain agent (gabapentin, pregabalin, amitriptyline) use. For participants in the treatment arm, amount of local anaesthetic infused will also be recorded.

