14.3 Sample size

'Good' pain control is defined as \leq 3 on a 0-10 NRS (66). Feasibility trial participants in the control arm reported 'freedom from pain' (defined as NRS \leq 3, or pain \leq 'mild' on a 4-point Verbal Rating Scale) 61.7% of the time in the first 5 postoperative days. Treatment arm participants reported 'freedom from pain' 76.8% of the time, a relative improvement of 24.5%. Using a more conservative (but still clinically important) relative improvement of 20% between arms results in a sample size of 299 participants per arm for 90% power when using a two-sample test for proportions with two-sided 5% alpha. In our feasibility trial, 45 of the 49 participants (92%) provided primary outcome data (defined as a participant providing outcome data for pain in >50% of possible timepoints). To account for this, a sample size of 650 is required.

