15.1 Main Analysis

For the statistical analysis of the primary outcome (proportion of 'successes' and 'failures' of pain control in the first 5 postoperative days for each participant, as defined in Section 14.3), we will use the intention-to-treat population and fit a multilevel logistic regression model, with the minimisation variables and condition (PAD or diabetes) as fixed-effect covariates and with random centre effects, to test for a difference between treatment arms at a 5% two-sided alpha level. Secondary outcomes will be analysed using similar multilevel regression models depending on the type of outcome (see Table 8) with the same covariate adjustments using the intention-to-treat principle. We will account for possible 'truncation by death' in sensitivity analyses. Additional secondary analyses considering the level of intervention fidelity will also be undertaken, including successful placement of the PNC, the PNC remaining in place for 5 days, and the local anaesthetic being infused within the dose and

rate ranges specified in the protocol for 5 days. All treatment effects will be reported as point estimates with 95% confidence intervals and p-values.

Table 8 Summary of Analysis for Secondary Outcomes

Outcome	Measure	Time frame	Analysis
Average pain	NRS	5d	Linear regression of median or mean (adjusted for baseline)
Overall satisfaction with analgesia	Likert scale	5d	Linear regression of transformed measure (if appropriate)
Total opioid use	Morphine equivalents	5d	Linear regression (adjusted for baseline)
Opioid side effects	Frequency and severity of symptoms	5d	Linear regression of transformed measure (if appropriate)
Surgical site infection	Proportion of people with infection	30d	Logistic regression
Delayed wound healing	Proportion of people with delay	30d, 6m	Logistic regression
Residual limb surgery	Proportion of people with surgery	30d, 6m	Logistic regression
Phantom limb pain	NRS	3m, 6m	Linear regression
Chronic stump pain	NRS	3m, 6m	Linear regression
Health utility/QoL	EQ-5D-5L	3m, 6m	Linear regression of transformed measure (adjusted for baseline)
Depression	HADS	3m, 6m	Linear regression of transformed measure (adjusted for baseline)
Prosthesis fitting	Proportion of people using prosthesis Time to achieve fitting	3m, 6m	Logistic regression Cox regression

Level of independence	SIGAM grading	3m, 6m	(Ordered) logistic regression, tabulation
independence			
Mortality	Proportion of people dead	6m	Logistic regression

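### Opioid side effects are the only five-day outcome with no preoperative measurement: avoidable loss of precision, not bias

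*Protocol*

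**What the plan says.** Opioid side effects are a secondary outcome for the first five postoperative days (protocol synopsis, 5.2, 5.4). Section 5.4 has them assessed once a day after surgery. Section 12.1.3 puts "Frequency and severity of opioid side effects (61" in the daily postoperative list, and Table 2 row 22 has one mark, under the first five postoperative days.

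The baseline list in 12.1.1 contains preoperative pain, satisfaction with pain management and "Preoperative opioid and analgesic use", together with EQ-5D-5L and HADS. It contains no symptom or side-effect score.

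In Table 8 (section 15.1) the outcome is measured as "Frequency and severity of symptoms" and analysed by linear regression of the score, transformed if appropriate, with no baseline term. Secondary outcomes share the covariates of the primary model: the minimisation variables (planned amputation level, type of anaesthesia, preoperative pain score, site; section 14.1) and condition, with random centre effects.

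**The concern.** Part of the rationale for the catheter is that opioids cause harm. Section 4.1 names nausea and vomiting, constipation, sedation and pruritus as opioid effects. Participants may well be taking opioids before surgery: the protocol collects that use and adjusts total opioid use for baseline. Section 9.4 cites a median of 7 days from vascular assessment to amputation even in emergency admissions, so there is time for such symptoms to develop.

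A postoperative symptom score therefore mixes new symptoms with those brought into theatre. With no preoperative score, that variation between people stays in the error term unless the planned covariates capture it. A null result on this outcome would also be harder to interpret. No analysis plan can repair this later, because a score that was never collected cannot be adjusted for.

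**Working it through.** **1. Is it the only five-day outcome without a baseline?**

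| Five-day outcome | Preoperative value | Baseline term in Table 8 |
|---|---|---|
| Pain | Yes (12.1.1; Table 2 row 6) | Yes, for average pain |
| Satisfaction | Yes (5.4; 12.1.1; row 20) | No |
| Total opioid use | Preoperative use recorded (12.1.1; row 7) | Yes |
| Opioid side effects | None (12.1.1; row 22) | No |

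It is. The text of 5.4 and 12.1.3 agrees with the position of the mark in row 22, so this does not rest on how the table was read.

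**2. The plan's own figure.** The protocol gives no power or precision figure for opioid side effects. Its only calculation is for the primary outcome: a control rate of "61.7% of the time in the first 5 postoperative days" and a "relative improvement of 20% between arms", tested with a "two-sample test for proportions with two-sided 5% alpha", which "results in a sample size of 299 participants per arm for 90% power". This reproduces. With p1 = 0.617, p2 = 0.617 × 1.2 = 0.7404 and mean 0.6787,

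n per arm = [1.960 × √(2 × 0.6787 × 0.3213) + 1.282 × √(0.617 × 0.383 + 0.7404 × 0.2596)]² / 0.1234² = 299.

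Then 2 × 299 / 0.92 = 650. The 92% comes from "45 of the 49 participants (92%) provided primary outcome data"; the exact fraction gives 652. Nothing in this point changes these numbers.

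**3. What a baseline score would add.** Let ρ be the correlation between the preoperative and five-day symptom scores after the planned covariates. Adding the baseline multiplies the variance of the treatment effect by 1 − ρ², and the confidence interval width by √(1 − ρ²). The documents do not give ρ, so the range is an assumption.

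| ρ (assumed) | Variance factor | Variance cut | Width factor | Width cut |
|---|---|---|---|---|
| 0.1 | 0.99 | 1% | 0.995 | 0.5% |
| 0.2 | 0.96 | 4% | 0.980 | 2% |
| 0.3 | 0.91 | 9% | 0.954 | 5% |
| 0.5 | 0.75 | 25% | 0.866 | 13% |
| 0.6 | 0.64 | 36% | 0.800 | 20% |

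**4. Effect on the treatment contrast.** Symptoms present before surgery precede allocation. They raise the expected score equally in both arms and cancel in expectation from the difference. Any chance imbalance is already reflected in the confidence interval.

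**The case against.** The plan is consistent with itself, and comparing a secondary outcome measured only after treatment is valid in a randomised trial. That stands: nothing is misstated, and this is an improvement rather than the correction of an error.

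A reader might infer that existing symptoms are misclassified as treatment effects and distort the result. The documents do not support that. The absolute level of symptoms may be raised in both arms, but the contrast is unbiased.

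A reader might also turn the precision loss into a number of participants, using 299 per arm. That goes too far. The 299 was derived for the pain outcome, and the protocol gives no evaluable number for side effects. The correlation must also be the partial one: preoperative pain and type of anaesthesia may already explain part of postoperative nausea and sedation. A value near zero cannot be excluded, and the gain would then be trivial.

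Preoperative opioid use is already collected and could serve as a covariate, possibly in an analysis plan that is not shown here. This has force, and the fix uses it. It is an incomplete substitute, because section 4.1 says that age, renal function and polypharmacy make opioid effects unpredictable in this population.

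Table 8 also omits a baseline term for satisfaction, which does have a preoperative value. So collecting a baseline does not by itself lead to adjustment, and both edits are needed. Finally, whether every item of the symptom-distress scale cited as reference 61 suits patients before surgery cannot be checked from the protocol.

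**Conclusion.** The gap is real and lies in data collection, so it belongs in the protocol. Opioid side effects alone among the five-day outcomes have no preoperative value. The consequence is modest: an unbiased but possibly less precise comparison for one secondary outcome, and no way to separate new symptoms from those already present. With an assumed partial correlation of 0.1 to 0.6, the baseline would cut variance by 1% to 36% and interval width by 0.5% to 20%. The low end is negligible and the high end worthwhile; the documents do not show where the trial would fall. The primary outcome and the sample size of 650 are untouched. This is a cheap, optional improvement.

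**What to change.** - Add the same symptom questionnaire once to the baseline list in 12.1.1, and mark the baseline column of Table 2 row 22. Check first that its items can be answered before surgery, including by people not taking opioids.
- Change the Table 8 row for opioid side effects to linear regression of the transformed measure, adjusted for baseline.
- For participants already enrolled without the score, use a missing-baseline indicator. This is valid because whether the baseline is missing is settled before allocation and so is unrelated to arm. The precision gain comes only from those who have the score.
- In addition, adjust this outcome for preoperative opioid use. Its collection is already planned for every participant, so it costs only an analysis edit.

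The cost is one short form at a preoperative assessment that already takes pain, satisfaction, EQ-5D-5L and HADS, plus one case report form page and a protocol amendment. The downside is slightly more questionnaire burden before surgery.
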